**Testing a Training Program That uses Virtual Reality Technology to Improve Children's
Pedestrian Behaviors: A Randomized Controlled Trial**

#NCT-03960047

Sept 1 2019

TITLE

Testing a Training Program That uses Virtual Reality Technology to Improve Children's Pedestrian Behaviors: A Randomized Controlled Trial

NCT-03960047

SETTING

We focus on midblock crossing on two-lane bidirectional roads, without nearby traffic signals or crosswalks.

For SS-T sessions, a road has been identified (50 km limit) that provides opportunity for training in *where* and *how* to cross in the same types of road situations to be presented in VR-T. Traffic volume was recently measured for 7 days and varied from light (8 cars/min) to heavy (16 cars/min).^{13,30} This range for traffic volume will occur in VR-T.

For VR-T sessions, these occur in the VR lab at UG campus.

For pre and post measures, for all groups these occur in two settings: **(a)** street side (designated as "Field" below) with naturally varying traffic (children indicate where and how they will cross but do not do so), **(b)** in the VR lab in which children cross the virtual street in traffic using a gaming controller.

Note that the pre/post Field measures will be taken at two locations along the *same* road (randomized order, with one used for pre and the other for post), which controls for familiarity and minimizes risk of large variation in traffic volume between pre/post measures. The road is nearby the VR lab, which allows children to complete pre-test VR *and* Field measures during the *same* visit to UG; the same will occur for post-test measures. Posted speed is 50 km, which means traffic conditions to be tested on are ones that pose risk of severe injury at these ages.^{13,57}

TESTING PROTOCOL

Pre/Post measures for Where and How to Cross

[Note that pre- and post- measures are the same, and all children, regardless of group, complete all measures.]

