Field Measures. For *where* to cross measures, the child selects the safest location to cross in 3 different street side situations (parked cars, hill, blind curve). For *how* to cross measures: the child stands 1 foot from the curb, with a pressure sensitive step plate in front of him (it connects to a laptop; a clear plastic wall prevents entry into the street), and completes a '2 step procedure' (based on observed traffic, take 2 steps forward, corresponding to initiating a street crossing;^{23,58} from this we estimate crossing measures. [NOTE: Street side testing is video recorded so traffic and crossing measures can be computed later; the PI has used this procedure before.⁵⁹]

VR Measures. The same measures as for Field, except completed within a virtual street environment.

Pre-Training Activities & Measures

VR-T. An initial Orientation and Movement-Control Training Module ensures all children are practiced with using the controller to navigate in the 3-D world to the same motor skill level, *before* starting pedestrian training. The controller allows them to vary their path, direction, and speed of walking and crossing.

SS-T. Children's average walking speed for crossing is determined⁵⁸ and then, in combination with video taken street side, is used to estimate crossing measures – so they do not cross in traffic, but only give initiation judgements. This is a common approach that the PI has used before.⁵⁹

Training Programs [All program decisions were informed by pilot testing.]

Each includes 6 training sessions of 30 minutes (2% of our pilot sample needed a break) and addresses *where* and *how* to look and cross. Performance is tracked on a trial-by-trial basis, and errors result in repetition of teaching trials, resulting in more training on skills they lack than those they have. Difficulty level generally increases over sessions as children acquire skills.

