VR-T. Children experience trials from each of three training modules that are organized logically for how one crosses: **(1)** deciding *where to cross* (component skills: identify a safe place with parked cars, traffic on hills, traffic on blind curves); **(2)** *effective looking* (component skills: left-right-left, always left as one enters the road); **(3)** *how to cross safely* (component skills: check traffic in both directions, select larger gaps, start right in when car back bumper passes). On each trial, the computer talks and provides immediate feedback on performance so children know if they safely completed the trial (e.g., “Great job”) or what they did that was unsafe and why (replays of what the child did are shown and explained), and what to do instead. A component skill is tested (with explanatory feedback given for failures) until the child achieves at least 80% success over a minimum of 5 trials or completes 15 trials. They then move on to test another component skill, with failed component skills retested in a future session. Over sessions, they get repeated training on all modules and component skills, but repetition focuses mostly on skills they still need to achieve.

SS-T. This program is grounded in behavior theory (modeling, reinforcement) and modeled after Kerbcraft⁶⁰ a program shown to improve children’s safe crossing behaviors. The program also includes *where* and *how* content and is organized similarly to VR-T (modules, teach component skills, immediate feedback). Over sessions, they get training on all modules and component skills, with repetition focusing on weaker skills.

STATISTICAL ANALYSIS PLAN

The CONSORT flowchart diagram will guide all reporting of results and an intention-to-treat analysis will be conducted, as appropriate.

Covariates

Summary statistics will be computed for baseline and demographic characteristics. When imbalances occur between groups, despite randomization, these variables will be included as covariates. Likely covariates include: (a) Child age; (b) Child Pedestrian Experience questionnaire data (parent report), which yields average weekly distance walked and other potential covariate indices;⁶⁸ (c) # of days between pre- and post- tests; (d) family income.

Primary Analyses

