Behaviors. We will document the baseline characteristics of each of the 3 groups (age, sex, walking experience, days between pre- and post- tests, family income, and traffic volume for field measures). We will produce point estimates and confidence intervals for the mean difference between pre- and post-immediate scores (i.e., change scores) for each group and each *where* (1 score), *how* (3 scores), and *consequence* (2 scores) outcome. We will then use linear regression of change score on group adjusting for covariates. We will extend this approach to multivariate (modeling multiple outcomes) linear regression incorporating all of the outcomes into one model and employing an adjustment for multiple comparisons. We will include interaction terms between group and sex to determine if child sex modifies program effects. An intention-to-treat approach will be followed. The goal is to assess for immediate gains following program completion in our outcomes (for Sustainability see Secondary Analyses).

Secondary Analyses

Behaviors. These will examine pre- to post-immediate changes in *Component Skills* performance (e.g., *where*: selecting safe location with parked cars) and examine from post-immediate to post-2 months later (to assess for sustainability of effects), comparing pre to post scores using the same approach as above.

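### The primary change-score regressions do not specify each outcome's own pre-test score as a covariate, so valid group contrasts may be less precise than the data allow

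*Combined protocol and SAP*

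**What the plan says.** Under Primary Analyses (Behaviors), the SAP first promises "point estimates and confidence intervals for the mean difference between pre- and post-immediate scores (i.e., change scores) for each group", covering one *where* score, three *how* scores and two *consequence* scores. The between-group step follows: "We will then use linear regression of change score on group adjusting for covariates". That model is then extended to a joint model of all outcomes with a multiplicity adjustment, and to group-by-sex interactions. Under Secondary Analyses, component skills are handled in the same way.

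The Covariates section supplies the adjustment rule: "Summary statistics will be computed for baseline and demographic characteristics", and then "When imbalances occur between groups, despite randomization, these variables will be included as covariates". The list that follows is open-ended: "Likely covariates include: (a) Child age; (b) Child Pedestrian Experience questionnaire data (parent report), which yields average weekly distance walked", with the interval between tests and family income also named. The baseline characteristics to be documented are "age, sex, walking experience, days between pre- and post- tests, family income, and traffic volume for field measures". Neither list names the pre-test value of the outcome.

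That value will exist. The Testing Protocol states that "pre- and post- measures are the same, and all children, regardless of group, complete all measures", and the VR measures are described as "The same measures as for Field, except completed within a virtual street environment". So each child should have a pre-test score in both settings.

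**The concern.** A change score subtracts the whole pre-test score from the post-test score, which fixes the post-on-pre coefficient at 1. If the true slope is lower, pre-test variation is over-subtracted and stays in the residual as noise. Entering the pre-test score lets the data set the coefficient.

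The documents give some reason to expect a slope below 1, though this is inference. Both programs concentrate repetition on weaker skills, so low starters have the most to gain. The Field *where* measure uses only three situations. Field testing takes place in naturally varying traffic, at different locations before and after.

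At stake is the precision of the between-group contrasts, across six primary scores with a multiplicity adjustment and sex interactions. The within-group intervals for mean change are not affected.

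**Working it through.** **Inputs from the documents.** The outcome is post-immediate minus pre. There are three groups and 1 + 3 + 2 = 6 primary scores, and pre-test scores are planned for every child. The plan gives no sample size, SD, pre-post correlation, alpha or allocation ratio, so it has no figure to reproduce. Everything numerical below rests on assumed inputs.

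**Variance formulas.** Set the pre-test SD to 1, the post-test SD to k and the within-group correlation to r, so the slope is b = rk.

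- Change score: 1 + k² − 2rk
- Change score with the pre-test score added: k²(1 − r²)
- Difference: 1 − 2rk + r²k² = (1 − b)², which is zero only at b = 1

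**Equal SDs (k = 1).** The ratio of adjusted to planned variance is (1 − r²)/(2 − 2r) = (1 + r)/2. The one-degree-of-freedom cost for q covariates and three groups is 1 + q/(N − 3 − q − 1). At an assumed N = 90 with q = 1, this is 1 + 1/85 = 1.012.

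| r | variance ratio | planned SE larger by | ratio net of the degree of freedom, N = 90 |
|---|---|---|---|
| 0.3 | 0.65 | 24% | 0.66 |
| 0.5 | 0.75 | 15% | 0.76 |
| 0.7 | 0.85 | 8% | 0.86 |
| 0.9 | 0.95 | 3% | 0.96 |

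If the adjusted analysis had 80% power (two-sided 0.05, assumed), the change-score analysis would have about 62%, 68%, 73% and 78%.

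**Unequal SDs.**

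- k = 0.7, r = 0.3: (0.49 × 0.91)/(1 + 0.49 − 0.42) = 0.446/1.07 = 0.42.
- k = 1.3, r = 0.7 (slope 0.91): (1.69 × 0.51)/(1 + 1.69 − 1.82) = 0.862/0.87 = 0.99. Net at N = 90 this is 0.9907 × 1.0118 = 1.002, so break-even.

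**Validity.** In a simulation with 30 per group, no effect and 20,000 trials per cell, type I error was 0.049–0.050 for the change score and 0.048–0.050 with the pre-test score added. With 50 per group and a true difference of 0.50, both estimators averaged about 0.50.

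**Robustness.** Suppose another covariate is already in the model, correlated 0.2–0.4 with both pre and post. Adding the pre-test score still gives ratios of 0.58–0.66, 0.68–0.78 and 0.79–0.90 at r = 0.3, 0.5 and 0.7. In three assumed cases with slopes or SDs differing by arm, the ratios were 0.67–0.76 between unlike arms and 0.49–0.67 between like arms.

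**What the imbalance rule might recover.** If pre-test scores are not screened, it recovers none of the gain. If they are screened, simulation with 30 per group gives:

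- p < 0.05: 19% of the gain
- p < 0.10: 31–33%
- p < 0.20: about half
- largest pairwise standardized difference above 0.25, 0.2 or 0.1: 90–91%, 95–96% or about 100%

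With 100 per group, the last three thresholds give 48–51%, 69–70% and 97%.

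**Reporting scale.** Change is post minus pre. With pre in the model, switching from post to change only lowers the pre-test coefficient by 1. A numerical check of the group-by-sex model gave identical group and interaction coefficients on both scales.

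**Joint model.** If each outcome's equation has its own pre-test score, the equations no longer share one design, and joint inference becomes approximate. A simulation with 6 outcomes, three equal groups, r = 0.5, between-outcome correlation 0.4 and no effect used a plain chi-square Wald test of group at nominal 5%. It rejected about 12–16% of trials at 20 per group and 9–11% at 30 per group. Keeping a shared design with all six pre-test scores avoids this, at a variance factor of 1 + 6/80 = 1.075 at N = 90. If Field and VR are scored separately, 12 scores give 1 + 12/74 = 1.16.

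**The case against.** The strongest reply is that the planned analysis is already sound: randomization makes the change-score contrast unbiased, and its error rate is right. That stands in full. A reader might infer that regression to the mean or chance baseline differences bias the comparison, but nothing in the documents supports that in a randomized trial.

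Second, a reader might infer that covariates enter only when imbalanced, so that the pre-test score is shut out. The text does not say so. It says imbalanced variables will be included, its list is open, and the primary model adjusts for covariates without stating a condition. The list even includes the interval between tests, which is not a baseline characteristic. Pre-test scores could also count as baseline characteristics. What stands is that the plan leaves their use, and the threshold for imbalance, unspecified.

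Third, the gain is not free. Near slope 1 it is nil or very slightly negative, and in the joint model outcome-specific covariates bring an inference problem that must be handled. Both points stand and shape the fix. Neither removes the case for adjustment in the single-outcome regressions.

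**Conclusion.** The point holds as a cheap improvement in precision. The omission and the algebra are certain; the practical size for this trial is not. With equal SDs and correlations of 0.3 to 0.9, the planned standard error is about 24% down to 3% larger than it need be. If post-test SDs are smaller than pre-test SDs the loss can be greater, and near slope 1 it vanishes. A reader might infer that the trial is underpowered as a result; with no sample size, SD or correlation given, the documents cannot show that. The imbalance rule could recover anything from none to nearly all of the gain, depending on whether pre-test scores are screened and at what threshold. The precision of the main comparison should not depend on an undefined rule.

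**What to change.** In each single-outcome between-group regression of pre to post-immediate change (primary outcomes, group-by-sex models, component skills), include the pre-test score for the same outcome and setting as a mandatory covariate, whatever the observed balance. Change can stay the reported scale.

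Base confirmatory between-group inference on these per-outcome tests, with the planned multiplicity adjustment. For the joint model, choose one of two routes in advance:

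- use outcome-specific pre-test scores with a small-sample or resampling-based (for example permutation) reference distribution, not a plain chi-square Wald test; or
- keep a shared design containing all pre-test scores and accept its degrees-of-freedom cost.

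No change is proposed for the within-group intervals or for the analysis from post-immediate to two months.

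The cost is a short SAP addition, including the joint model's inference method, and no new data. Each single-outcome equation loses one degree of freedom, a variance factor of about 1.018, 1.012 or 1.007 at assumed total N of 60, 90 or 150, before any gain. The addition should be fixed before outcome data are seen.

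### Does leaving Field or VR unnamed for the six primary scores leave the primary analysis and its multiplicity control broken?

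*Combined protocol and SAP*

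**What the plan says.** The Setting section describes the testing: "For pre and post measures, for all groups these occur in two settings". In Field, "children indicate where and how they will cross but do not do so"; the other setting is "in the VR lab in which children cross the virtual street in traffic using a gaming controller". The note opening the Testing Protocol has every child take every measure, whatever the group. The VR Measures paragraph defines the VR tests as "The same measures as for Field, except completed within a virtual street environment".

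Primary Analyses (Behaviors) counts one where score, three how scores and two consequence scores. The model is stated as "We will then use linear regression of change score on group adjusting for covariates". It is then extended to a multivariate regression holding all the outcomes, with an unnamed adjustment for multiple comparisons. No setting is attached to any score, and there is no group-by-setting term. The section's one reference to a test setting is traffic volume for the Field measures, listed as a baseline characteristic.

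On training, "For VR-T sessions, these occur in the VR lab at UG campus", while SS-T uses a real road. On program length: "Each includes 6 training sessions of 30 minutes". Under Pre-Training Activities, in the VR-T paragraph: "An initial Orientation and Movement-Control Training Module ensures all children are practiced with using the controller to navigate in the 3-D world".

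**The concern.** Two settings and one unlabelled list of six scores leave several readings open: Field only, VR only, an average of the two, or each analysed separately. If the reading were picked after group results were known, the better-looking setting could be reported, and an adjustment sized for six would not protect twelve tests.

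The setting is not neutral here. VR-T children spend 6 x 30 = 180 minutes in the medium of the VR test, and SS-T children train at the roadside, the medium of the Field test. A VR-T gain seen only on VR scores might be partly ease with the controller, and the VR-T versus SS-T comparison could lean either way with the setting reported. The orientation module adds a doubt: it appears under VR-T, and its timing relative to the VR pre-test is not given.

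**Working it through.** The documents state no sample size, significance level, adjustment method or family size, so there is no figure of theirs to reproduce. The level (5%, two-sided) and Bonferroni are assumed below.

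**Counts.** Scores per setting: 1 + 3 + 2 = 6. Two settings: up to 12. If the consequence scores exist in one setting only: 4 x 2 + 2 = 10. Three groups give three pairwise contrasts: 6 x 3 = 18 or 12 x 3 = 36 tests.

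**Error per group contrast if the family and the adjustment do not match** (independent tests):
- 12 tests at 0.05/6: 1 - (1 - 0.00833)^12 = 9.6%; upper bound 12 x 0.05/6 = 10%.
- 10 tests at 0.05/6: 1 - (1 - 0.00833)^10 = 8.0%.
- 12 tests at 0.05/6 with assumed correlations of 0.5 to 0.8 across settings and 0.3 to 0.5 across scores: 6.7% to 8.6% by simulation.

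**Error if they do match:**
- 6 tests at 0.05/6: 4.9%.
- 12 tests at 0.05/12: 1 - (1 - 0.00417)^12 = 4.9%.

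The inflation therefore comes entirely from sizing the adjustment for six and applying it to twelve. The plan does not say to do that: it adjusts a model that holds all the outcomes.

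**Picking the better setting for one score.** At an unadjusted 5%, the error is 9.1% or 7.8% for an assumed cross-setting correlation of 0.5 or 0.8. This too supposes that the promised adjustment is ignored.

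**Price of always analysing both settings.** The per-test level falls from 0.05/6 = 0.0083 to 0.05/12 = 0.0042, with critical values 2.638 and 2.865. A test with 80% power at the first has Phi(2.638 + 0.842 - 2.865) = Phi(0.615) = 73% at the second. Keeping 80% needs ((2.865 + 0.842)/(2.638 + 0.842))^2 = 1.135, about 13.5% more children.

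**Would a group-by-setting term isolate familiarity?** Assume 50 per arm and a pre-post correlation of 0.5. The standard error of a group difference in change is sqrt(4 x 0.5/50) = 0.200 SD. With an assumed correlation of 0.5 between settings, the standard error of the interaction is 0.200 x sqrt(2 x 0.5) = 0.200 SD, and the 95% half-width is 1.96 x 0.200 = 0.39 SD. Precision is not the main limit. Field records initiation judgements with estimated crossings, whereas VR records completed virtual crossings. A gain confined to VR could be ease with the equipment, or learning that the Field procedure does not register. The term cannot tell these apart at any sample size.

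**The case for a change.** The strongest case for a change is that the omission is real and cheap to close. Six scores are counted, two settings are tested, and the two textual cues (all outcomes in one model; traffic volume for Field) do not settle which is meant. Each program trains in one of the test media, so the choice could move the comparison of most interest.

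The omission stands, and so does the caution that a VR-only gain should not be presented as safer pedestrian behaviour in general. Nor can it be said that the promised adjustment would keep a familiarity effect harmless. Under the same assumptions (50 per arm, pre-post correlation 0.5), a pure familiarity gain in a single VR score would be declared significant at 0.05/36 in 4.5% of trials for 0.3 SD and 24% for 0.5 SD. If all six VR scores shared it (assumed correlation 0.3 to 0.5 between scores), at least one would be declared in about 17-20% and 59-68%. The documents give no size for such a gain, so this neither shows a fault nor rules one out.

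What does not stand is the step from omission to defect. No stated rule gives a wrong answer when followed. Requiring separate analyses and a family of up to 36 is one preference among valid ones; naming one primary setting is equally sound and avoids the power loss. That no listed covariate addresses familiarity carries little weight, because training medium is fixed by arm and no baseline covariate could. The orientation text says that all children are practised. The neighbouring SS-T paragraph covers walking speed used to estimate crossings, a step the Field test needs in every group, so those labels plausibly mean mode rather than arm. The timing of the module is a separate, minor clarification.

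**Conclusion.** The plan leaves the setting and the multiplicity family unstated. This is a gap in detail that a competent analyst fills before comparing groups: decide whether the scores are Field, VR, pooled or separate, let the adjustment cover the resulting set, and show results by setting. Done that way, family-wise error per contrast stays at 5% or below; the 8-10% figures need an adjustment that does not match the tests. The choice between one setting and both is a fair trade-off, about 80% against 73% power under Bonferroni at an assumed two-sided 5%. The training-medium issue belongs in the interpretation of VR-T versus SS-T, and an added interaction term would not resolve it. No change to the plan follows. This rests on reading the promised adjustment as covering every outcome in the multivariate model, and on the choice of setting being made before group results are seen.

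### Intention-to-treat is promised, but the primary change-score regressions have no missing-data method and no pre-score term, so under standard fitting they become complete-case analyses

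*Combined protocol and SAP*

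**What the plan says.** Under Primary Analyses (Behaviors), the outcome is the "mean difference between pre- and post-immediate scores (i.e., change scores) for each group", for six scores: one for where to cross, three for how, and two for consequences. The modelling has two stages. The first is "We will then use linear regression of change score on group adjusting for covariates". The second is a multivariate linear regression "incorporating all of the outcomes into one model", with an adjustment for multiple comparisons. The same paragraph states "An intention-to-treat approach will be followed". The opening of the Statistical Analysis Plan is weaker: "an intention-to-treat analysis will be conducted, as appropriate".

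On covariates, the plan says "When imbalances occur between groups, despite randomization, these variables will be included as covariates". The likely candidates are child age, pedestrian experience, the interval between pre- and post-test, and family income. The pre-test score is not among them.

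The plan does not mention missing data, dropout, imputation, a likelihood-based model or a sensitivity analysis. It does not define which randomised children enter the models.

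**The concern.** A change score needs both a pre and a post value, so a child who is never post-tested has no outcome in any model. Standard multivariate linear regression also drops a child who lacks any one outcome or covariate, even if the other five scores are complete. The interval between tests, a likely covariate, has no value for a child without a post-test. Fitted in the usual way, the stated models therefore analyse completers only, although the same paragraph promises intention-to-treat.

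There are two things at stake. The first is precision: a lost video or step-plate record can remove a child from the joint model for all outcomes. The second is bias. Children with low pre-scores tend to show larger gains. If low scorers go missing more from one group than from another, the remaining children in that group start higher and appear to gain less. With no pre-score in the model, nothing corrects for this.

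**Working it through.** The documents give no sample size, SD, effect size or dropout rate, so there is no planned figure to reproduce. All rates below are assumptions.

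**1. Children kept in the joint model.** The six scores come from Primary Analyses (1 + 3 + 2). The Setting section says that VR and Field measures are taken at the same visit. The Testing Protocol derives the Field crossing measures from one step-plate and video procedure. Let d be the share missing the whole post-test visit, q the share of records lost singly and independently, and m the number of separate records behind the six scores.

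- Share kept = (1 − d)(1 − q)^m
- SE relative to full data = 1/√(share kept)

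Whole visits only (d = 10%, q = 0): 0.90 is kept in the single-outcome models and 0.90 in the joint model. The joint model loses nothing extra.

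Single losses only (d = 0):

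| Assumption | q = 2% | q = 5% |
|---|---|---|
| One score alone (m = 1) | 98.0% kept, SE ×1.01 | 95.0% kept, SE ×1.03 |
| Six scores from two records (m = 2) | 96.0% kept, SE ×1.02 | 90.3% kept, SE ×1.05 |
| Six scores lost independently (m = 6) | 88.6% kept, SE ×1.06 | 73.5% kept, SE ×1.17 |

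At q = 5%, the SE of the joint model relative to a single-outcome model is √(0.95/0.9025) = 1.03 with two records and √(0.95/0.735) = 1.14 with six.

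For a comparison assumed to have 80% power with full data (two-sided 5%), power is Φ{(1.960 + 0.842)√(share kept) − 1.960}. This gives 76% at 90.3% kept and 67% at 73.5% kept.

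**2. Bias of the complete-case change score.** Take pre and post with SD 1 and correlation ρ. Given the pre-score, expected change is a constant plus the group effect minus (1 − ρ) × pre. If missingness depends only on group and pre-score, then:

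- Bias = −(1 − ρ) × (difference between groups in completers' mean pre-score)

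Assume that in one group the probability of a missing post-test is 1/(1 + exp(1.6 + pre)), which averages 20.7%, and that loss in the other is random. Completers in the first group then have a mean pre-score of +0.179 SD. The bias is −0.7 × 0.179 = −0.125 at ρ = 0.3, −0.5 × 0.179 = −0.089 at ρ = 0.5, and −0.3 × 0.179 = −0.054 at ρ = 0.7.

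A simulation of 400,000 children with a true difference of 0.50 agrees:

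| Missing post-tests (about 20%) | Complete-case change score | Same, adjusted for pre-score | Using every child's pre-score |
|---|---|---|---|
| Completely random | 0.49 to 0.50 | 0.50 | 0.49 to 0.50 |
| Depends on pre-score equally in both groups | 0.50 | 0.50 | 0.50 |
| Depends on pre-score in one group only | 0.37 to 0.44 | 0.50 | 0.50 |

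(Ranges are over ρ = 0.3 to 0.7; departures of under 0.01 from 0.50 are simulation error.)

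A second simulation assumed 5% dropout in one group and about 21 to 24% in the other, with a logit slope of 0.5 to 1.0 per SD of pre-score. It gave a complete-case bias of −0.03 to −0.15 SD, and a bias near zero once the pre-score was used.

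**The case against.** The strongest reply is that the plan is silent on missing data and nothing in it prescribes complete cases. A reader might infer that only children with every score will be used, so that intention-to-treat cannot be delivered. The documents do not support that. They name a model, not an analysis set, and the same regression can be fitted after imputation. With complete data there is no conflict at all. This part of the reply stands.

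Four further limits also stand:

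- **Stopping training is not missing the post-test.** The Testing Protocol intends all measures for every child in every group, so a child who leaves the six-session program may still be tested. That is an intention to collect data, though, and gives no rule for data that are missing.
- **Large sample losses should not be read into the joint model.** Same-visit testing makes losses cluster, so 73.5% is a worst case for six scores. Counting twelve scores gives 0.95^12 = 54.0%, but that requires Field and VR to be scored separately, which the plan does not say.
- **The first-stage regressions are less exposed.** If fitted for each outcome, they keep any child who has that outcome. They still lose every child without a post-test.
- **Loss of weaker children does not by itself bias the comparison.** The pattern must differ between groups. The two described programs have the same number and length of sessions, and the third group's activity is not described, so the documents give no direct evidence of differential loss. In the simulated case a complete-case model with the pre-score was also unbiased, so that bias comes from omitting the pre-score while analysing completers.

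The reply does not show how the promised population would be analysed once a score is missing. It also does not change the fact that the listed covariates leave out the variable that would remove the bias.

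**Conclusion.** The point holds in a conditional form. As specified and fitted in the standard way, the primary models are complete-case analyses of change without the pre-score, and the plan gives no route from them to intention-to-treat when scores are missing.

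The cost in precision ranges from nothing beyond the single-outcome models (whole-visit loss) to about 10% to 26% of children removed from the joint model (5% single-record loss, from two clustered records to six independent scores). The bias ranges from none to about 0.03 to 0.15 SD; the upper values need roughly 20% dropout in one group, with dependence on the pre-score that differs between groups. These sizes rest on assumed rates, correlations of 0.3 to 0.7, and missingness explained by group and pre-score. If missingness also depends on the unseen post-score, using the pre-score would not fully remove the bias.

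This is more than a missing detail, because the remedy replaces the stated change-score model with one that keeps partial data and removes that bias. It should be changed, but it does not show that the trial's result would be wrong.

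**What to change.** 1. Define the primary analysis set as every randomised child with any score, analysed in the allocated group.
2. For each score, make the primary analysis a likelihood-based repeated-measures model with the pre and post-immediate scores as responses, a common baseline mean across groups and an unstructured covariance. The 2-month value may be added for the secondary sustainability analysis.
3. If the joint multivariate model is kept, fit it after multiple imputation using all pre-scores, group and covariates, and include the pre-score in the model. The interval between tests needs its own rule, because it has no value for a child who is never post-tested.
4. Keep the complete-case change-score regression as a sensitivity analysis.

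The cost is revised SAP wording, modest extra programming and reliance on a missing-at-random assumption. The change does not recreate the information lost with a missed post-test. A child with only pre-scores mainly helps to correct for baseline-related loss, while the gain in precision comes from children who have lost single scores.
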